### **13.6. Analyses of Exploratory Endpoints**

Exploratory PD and clinical outcomes data for each timepoint will be listed by subject and summarized by treatment group separately for Population 1 (TDT) and Population 2 (NTDT) as appropriate. Correlations between PK and the exploratory endpoints may be assessed.

Descriptive statistics will be computed as appropriate.

Summary statistics for QoL scores from the prespecified domains will be calculated at each administration timepoint. Summary statistics will also be calculated for change from baseline in each score at each administration timepoint.

Exploratory PD outcomes will be based on the PD analysis set, and QoL outcomes will be based on the safety and per protocol sets.

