7.3 Exploratory Objectives

7.3.1 Population 1: Transfusion-dependent β -Thalassemia

The exploratory objectives in TDT subjects are:

- To characterize the pharmacodynamic (PD) profile of IMR-687 versus placebo with respect to erythropoiesis, iron metabolism, and hemolysis.
- To evaluate the effect of IMR-687 versus placebo on the proportion of subjects who are transfusion independent.
- To evaluate the effect of IMR-687 versus placebo on time to and duration of reduction in RBC transfusion burden.
- To evaluate the effect of IMR-687 versus placebo on functional and health-related quality of life (QoL).
- To evaluate responses to IMR-687 per genotypes in subjects with TDT.

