7.3.2 Population 2: Non-transfusion-dependent β -Thalassemia

The exploratory objectives in NTDT subjects are:

- To characterize the PD profile of IMR-687 versus placebo with respect to erythropoiesis, iron metabolism, and hemolysis.
- To evaluate the effect of IMR-687 versus placebo on functional and health-related QoL.
- To evaluate the effect of IMR-687 versus placebo on β-thalassemia-related symptoms and severity.
- To evaluate responses to IMR-687 per genotypes in subjects with NTDT.

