10.1.9 Quality of Life Assessments

Quality of life will be assessed using the TranQOL and SF-36 QoL tools in the TDT population and the NTDT-PRO and SF-36 QoL tools in the NTDT population.

The TranQOL (Klaassen 2013; Klaassen 2014. See protocol section 16.) is a disease-specific QoL measure for children and adults with thalassemia major. It has four versions: (i) a child self-report; (ii) an adult self-report; (iii) a parent self-report (measuring the impact of the disease on the parent), and (iv) a parent proxy report (measuring the child’s QoL). The questionnaire length ranges from 29 items (child) to 39 items (parent). The questions are grouped into 4 domains: physical health, emotional health, family functioning, and school and career functioning. The adult and parent self-report questionnaires include a fifth category on sexual activity which is only one item. For this study, only the adult self-report will be used which includes 36 items and an open-ended question: “Was there anything else that bothered you?”. The mean TranQOL score for each domain ranges from 0 to 100 with higher scores indicating higher QoL. Derivations for domain scores are specified in Section 13.6.6.1. A within-patient clinically meaningful change from baseline was defined as a ≥ 4 -point change for the TranQOL total score (Cappellini 2020). The criteria may be modified based on further research.

The SF-36 (Hays 2004. See protocol section 16.) is a 36-item, patient reported survey of patient health. The SF-36 consists of 8 scaled scores, which are the weighted sums of the questions in their section. Each scale is directly transformed into a 0 to 100 scale based on each scale having equal weight. The lower the score the more disability and the higher the score the less disability (i.e., a score of 0 is equivalent to a maximum disability and a score of 100 is equivalent to no disability). The 8 sections are: vitality, physical functioning, bodily pain, general health perceptions, physical role functioning, emotional role functioning, social role functioning, and mental health. Derivations for the scales and component scores are specified in Section 13.6.6.1. A within-patient clinically meaningful change from baseline was defined as 3.8–7.0-point improvement, based on the prespecified domain-specific cutoff values for the domains of the SF-36 questionnaire (Cappellini 2020).

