Proportion of subjects with an increase from Baseline of ≥ 1.0 g/dL in mean pre-transfusion Hb values or a Reduction in RBC	Week 12 to Week 24, Week 24 to Week 36, and Week 12 to Week 36	
 Cochran-Mantel Haenszel (CMH) analysis: Odds ratios (OR) (active arms vs.

Transfusion Burden ($\geq 33\%$ reduction) Endpoint at Weeks 12 to 24, Weeks 24 to 36, and Weeks 12 to 36 [using pre-transfusion Hb from the Historical Transfusion Burden and the Transfusion Burden CRFs]		placebo), 2-sided 95% CI, p-value 
 Summary of number and percentage of responders with difference in proportions (active arm-Placebo) and corresponding 2-sided 95% CI Forest plots of ORs, 2-sided 95% CIs, p-value – Higher dose vs. placebo, Lower dose vs. placebo
Mean change from Baseline in TranQOL quality of life tool	Weeks, 12, 24, and 36	Descriptive Summary
Mean change from Baseline in SF-36 quality of life (PCS and MCS domains and 8 sections)	Weeks, 12, 24, and 36	Descriptive Summary
Pharmacogenomic analyses of genes that may affect treatment response (including α -globin, gamma-globin Xmn1 polymorphism, and BLC11A)	NA	Descriptive Summary
Average number of days between transfusions	Over 36 weeks	Descriptive Summary

Table 12 Exploratory Endpoints – NTDT Population

Exploratory Endpoints	Time Points	Exploratory Endpoint Analysis
Proportion of subjects who are transfusion-free (independent) for ≥ 8 weeks during treatment	Over treatment time	CMH analysis: Odds ratios (active arm vs. placebo), 95% CI, p-value, difference in proportions (active arm-Placebo) and corresponding 95% CI will be provided
Proportion of subjects who are RBC transfusion-free (independent) over 36 weeks and other variables of transfusion burden	Over 36 weeks	CMH analysis: Odds ratios (active arm vs. placebo), 95% CI, p-value, difference in proportions (active arm-Placebo) and corresponding 95% CI will be provided
Mean change from Baseline in SF-36 quality of life (PCS and MCS domains and 8 sections)	Weeks, 12, 24, and 36	Descriptive Summary
Pharmacogenomic analyses of genes that may affect treatment response (including α -globin, gamma-globin Xmn1 polymorphism, and BLC11A)	NA	
 Descriptive Summary Subgroup analysis

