The TranQOL includes 36 questions spanning five domains. Questions 1 – 10 will be used to calculate Physical Health domain scores, questions 11 – 24 will be used to calculate the Emotional Health domain score, question 25 will be used to calculate the Sexual Activity domain score, questions 26 – 30 will be used to calculate the Family Functioning domain score, and questions 31 – 36 will be used to calculate the School and Career Functioning domain score. Each of the 36 questions has five possible responses which will be coded numerically. For all questions except for items 2, 4, 9, 16, 17, 25, 26, and 27, responses and corresponding numerical values are:

- 5 = Always
- 4 = Often
- 3 = Sometimes
- 2 = Almost Never
- 1 = Never
- -1 = Not Applicable

For the remaining 8 questions, responses and corresponding numerical values are:

- 1 = Always
- 2 = Often
- 3 = Sometimes
- 4 = Almost Never

- 5 = Never
- -1 = Not Applicable

Domain scores are calculated using the equation $100 \times (1 - [(\text{Sum of all scores in the domain} - \text{number of valid responses in the domain}) / (\text{number of valid responses in the domain} \times 4)])$. Scores of -1 are excluded from the calculation. Domain scores can only be calculated if <25% of the total number of questions in that domain are missing. Domain scores range from 0 to 100 where higher scores indicate higher QoL.

Descriptive statistics for the five domain scores will be reported at Baseline and Weeks 12, 24, and 36. Change from Baseline to each post-Baseline assessment will also be presented for each domain score.

The SF-36 includes 36 questions spanning 8 scales which are weighted sums of the questions in their section. Optum Health scoring software will be used to transform individual question responses to the scales which range from 0 to 100 where higher scores indicate less disability. The scales include Physical Functioning, Role Physical, Bodily Pain, General Health, Vitality, Social Functioning, Role Emotional, and Mental Health. The software will also calculate two overall scores, the Physical Component Score and the Mental Component Score.

Descriptive statistics for the eight scale scores and the two component scores will be tabulated at Baseline and at Weeks 12, 24, and 36. Change from Baseline to each post-Baseline assessment will also be presented for each scale and component score.

By-subject listings of TranQOL data and SF-36 data will be presented on the ITT Analysis Set.

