 - a. Date of Hb change from baseline value ≥ 1.0 g/dL – (Date of previous non-missing laboratory Hb value)
 - b. Note: The date of the previous non-missing laboratory Hb value may include baseline values.
3. For each subject, sum up all values from #2 above.

Mean Change from Baseline in NTDT-PRO and SF-36 Quality of Life Tools

Subjects in the NTDT Population will complete two questionnaires, SF-36 and NTDT-PRO, at Baseline and Weeks 12, 24, and 36.

Similar to the TDT Population, descriptive statistics for the eight scale scores and the two component scores of the SF-36 will be tabulated at Baseline and at Weeks 12, 24, and 36. Change from Baseline to each post-Baseline assessment will also be presented for each scale and component score.

The NTDT-PRO consists of eight items. Questions 1 and 2 assess tiredness with and without physical activity. Questions 3 and 4 assess weakness with and without physical activity. Questions 5 and 6 assess shortness of breath with and without physical activity. The final two items assess the overall severity and progression of thalassemia symptoms. Items 1 – 4 are grouped into the Tiredness/Weakness Domain and Items 5 – 6 are grouped into the Shortness of Breath Domain.

Scores for the 6 domain related questions range from 0 (no tiredness/weakness/shortness of breath) to 10 (extreme tiredness/weakness/shortness of breath).

The Tiredness/Weakness domain score will be calculated by averaging the responses to questions 1-4. The Shortness of Breath domain score will be calculated by averaging the responses to questions 5-6. If any responses are missing in questions 1-4 or 5-6 for the timepoint of evaluation, then the Tiredness/Weakness and Shortness of Breath domain scores cannot be calculated, respectively.

The total score will be calculated by averaging the responses to questions 1-6. If any responses are missing at the time point in question, then the total score cannot be calculated.

Descriptive statistics of the Tiredness/Weakness and Shortness of Breath domain scores and total score, and changes from Baseline, will be reported at Baseline and at Weeks 12, 24, and 36 by treatment group, as well as changes from the last assessment, i.e., from Week 12 to Week 24 and Week 24 to Week 36.

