The mean change from Baseline in the NTDT-PRO total score will be assessed using an ANCOVA model with Baseline value as a covariate. Summary statistics for observed values at Baseline and Week 24 and change from Baseline to Week 24 will be presented. LSMean estimates and 95% CIs will be presented for each active arm and placebo at Week 24. The LSMean difference estimates and associated 95% CIs and p-values at Week 24 will also be reported for each active arm compared to placebo and the combined active arms-Placebo. The Week 36 NTDT-PRO total score will be analyzed with a similar model, as will the NTDT-PRO T/W and SOB domain scores at Weeks 24 and 36.

By-subject listings of SF-36 data and NTDT-PRO data will be presented on the ITT Analysis Set.

Proportion of Subjects with an Increase from Baseline of $\geq 3\%$ in Mean HbF Over 12 Week Rolling Time Periods Endpoint

The proportion of subjects with increase from Baseline of $\geq 3\%$ in mean HbF values measured over 12-week intervals (from Day 2 to 85, Day 3 to 86, etc. through Day 170 to Day 253 (Week 36)) will be assessed using a CMH test. The number and percentage of responders and non-responders at each of the rolling time periods will be presented for each treatment group as well as ORs, 95% CIs, and p-values from the CMH tests. The difference in proportions (active arm-Placebo and the combined active arms-Placebo) and corresponding 95% CI will be also provided. Bar plots will be provided. The proportion of subjects with response in HbF, where a responder has an increase of $\geq 3\%$ at each of the rolling time periods compared to Baseline, Odds ratios, 95% CI, and p values will be displayed by treatment arm.

Proportion of Subjects with an Increase from Baseline of ≥ 1.0 g/dL in Mean Hb Over 12 Week Rolling Time Periods Endpoint

The proportion of subjects with increase from Baseline of ≥ 1.0 g/dL in mean Hb values measured over 12 week intervals (from Day 2 to 85, Day 3 to 86, etc. through Day 170 to Day 253 (Week 36)) will be evaluated using a Cochran-Mantel-Haenzel (CMH) test to compare the proportion of subjects who achieved improvement between the placebo group and each of the 2 active treatment arms (IMR-687 lower dose and IMR-687 higher dose) and the combined active arms. The number and percentage of responders and non-responders, ORs, 95% CIs, p-values from the CMH tests and the difference in proportions and corresponding 95% CI will be provided similarly to the HbF above.

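### TranQOL and SF-36 have descriptive summaries only, so the versus-placebo quality-of-life objective has no planned between-arm estimate in TDT, and in NTDT only through NTDT-PRO

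*SAP*

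**What the plan says.** SAP 7.3.1 and 7.3.2 state the same comparative objective for TDT and NTDT, worded for NTDT as "To evaluate the effect of IMR-687 versus placebo on functional and health-related QoL". The objective is exploratory.

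Four instrument-by-population analyses serve it:

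- **TranQOL, TDT.** The SAP Table 11 row "Mean change from Baseline in TranQOL quality of life tool" has a descriptive summary as its only method. SAP 13.6.6.1 adds: "Descriptive statistics for the five domain scores will be reported at Baseline and Weeks 12, 24, and 36", and change from baseline for each domain.
- **SF-36, TDT.** Table 11 and 13.6.6.1 give the same treatment to the eight scales and two component scores.
- **SF-36, NTDT.** Table 12 also lists a descriptive summary. SAP 13.6.6.3 says "descriptive statistics for the eight scale scores and the two component scores of the SF-36 will be tabulated at Baseline and at Weeks 12, 24," with Week 36 as the last visit.
- **NTDT-PRO, NTDT.** SAP 13.6.6.3 says: "The mean change from Baseline in the NTDT-PRO total score will be assessed using an ANCOVA model with Baseline value as a covariate". It reports least-squares mean differences from placebo, with 95% intervals and p-values, for each dose and for the combined doses. The total and both domain scores are modelled at Weeks 24 and 36.

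Protocol 13.6 plans summary statistics only for QoL: "Summary statistics will also be calculated for change from baseline in each score at each administration timepoint". It also says that exploratory outcomes are summarised by treatment group. SAP 13.0 restricts pairwise comparisons with placebo to places where they are specified.

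SAP 10.1.9 defines a meaningful within-patient change as at least a 4-"point change for the TranQOL total score". SAP 13.6.6.1 gives a scoring formula for the five TranQOL domains and none for a total.

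**The concern.** An objective worded against placebo calls for a planned contrast with placebo. For TranQOL and SF-36 the plan stops at tables by arm. A reader of the report would have to subtract mean changes, with no prespecified interval to show how uncertain the result is and no adjustment for chance baseline differences between small arms.

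Exploratory status does not explain the omission, because other exploratory endpoints in the same SAP do get a model. In TDT these are the PD markers, the number of transfusion events and mean pre-transfusion haemoglobin (13.6.6.1). In NTDT it is NTDT-PRO, which SAP 10.1.9 itself describes as a health-related QoL tool.

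The missing total score is a smaller gap of the same kind: the SAP's only stated TranQOL yardstick applies to a variable that the SAP does not produce.

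**Working it through.** **1. Is a contrast planned anywhere?** The documents give no power, sample size or alpha for any QoL endpoint, so there is no stated figure to reproduce. The check is a reading of every place that sets a QoL analysis.

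| Instrument, population | Planned method | Estimate versus placebo |
|---|---|---|
| TranQOL, TDT | Descriptive (Table 11, 13.6.6.1) | None |
| SF-36, TDT | Descriptive (Table 11, 13.6.6.1) | None |
| SF-36, NTDT | Descriptive (Table 12, 13.6.6.3) | None |
| NTDT-PRO, NTDT | ANCOVA (Table 12, 13.6.6.3) | Difference, 95% CI, p-value |

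Three of four have no contrast; in TDT it is two of two. The subgroup section (13.6.4.5), which includes the SF-36 component scores in NTDT, rules out inferential statistics and so adds none.

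**2. What would baseline adjustment add?** Let SD be the score's standard deviation and ρ the correlation between baseline and follow-up.

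- SD of the change score: SD × √(2(1−ρ)).
- ANCOVA residual SD: SD × √(1−ρ²).
- Variance ratio, ANCOVA to change score: (1−ρ²)/(2(1−ρ)) = (1+ρ)/2.

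The documents do not give ρ. At an assumed 0.5 the ratio is 0.75, and at 0.7 it is 0.85, so the variance is 15% to 25% lower. An unadjusted interval would be 1/√0.85 = 1.08 to 1.15 = 1/√0.75 times as wide.

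**3. How precise would the estimate be?** The half-width is t × SD × √(1−ρ²) × √(1/n₁ + 1/n₀), with n₁+n₀−3 degrees of freedom. The SD is not in the documents; 12 to 18 points is assumed.

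Residual SD runs from 12 × √(1−0.49) = 8.57 to 18 × √(1−0.25) = 15.59.

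| Active v placebo | Source of arm sizes | √(1/n₁+1/n₀) | t | Half-width, points |
|---|---|---|---|---|
| 30 v 20 | SAP 8.1.1 | 0.289 | 2.012 | 5.0 to 9.1 |
| 30 v 15, higher dose | 60 subjects, all at 1:2:1 | 0.316 | 2.018 | 5.5 to 9.9 |
| 24 v 16, higher dose | first 12 at 2:1, then 48 at 1:2:1 | 0.323 | 2.026 | 5.6 to 10.2 |
| 15 v 15, lower dose | 60 subjects, all at 1:2:1 | 0.365 | 2.052 | 6.4 to 11.7 |

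Power for a 4-point between-arm difference at two-sided 0.05 is about 14% to 35% with 30 v 20, and 12% to 30% for the two higher-dose rows. The 4 points is a within-patient threshold, borrowed here only as a yardstick.

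**4. How many contrasts would the fix add?** TDT: 3 scores × 2 visits × 3 comparisons = 18. NTDT: 2 × 2 × 3 = 12. Total: 30.

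**The case against.** The strongest reply is that little is lost. The objective is exploratory, the SAP matches Protocol 13.6, and the endpoint is defined as mean change from baseline, which is what the tables report. Arms are shown by treatment group with number, mean and SD, so a difference and an approximate interval can be recovered. By step 2 that interval would be only about 8% to 15% wider than an adjusted one, and by step 3 the adjusted one would rarely exclude a 4-point effect.

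Most of this stands, and it sets the severity. It also disposes of three stronger readings that a reader might infer:

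- That the QoL objective is never compared between randomised arms. NTDT-PRO is compared in NTDT.
- That the TDT objective cannot be answered against placebo. The tabulated summaries allow an unadjusted difference.
- That changes shared with placebo will be credited to the drug. The QoL sections plan no within-arm interval or test, and the placebo summaries stand alongside.

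What does not fall away is the inconsistency. A recoverable difference is not a planned one, agreement with the protocol does not bring either document up to the objective, and the SAP models comparable exploratory endpoints.

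A fair objection also applies to the total score: the documents give only a domain formula and a domain-level missing-item rule, so extending these to a total would invent a scoring rule.

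**Conclusion.** The point holds in limited form. TranQOL and SF-36 in TDT, and SF-36 in NTDT, have no planned between-arm estimate or interval, so the versus-placebo QoL objective has none at all in TDT and has one in NTDT only through NTDT-PRO. The TranQOL total score that carries the 4-point threshold is not derived. These conclusions rest on the text alone.

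The benefit of adding a model rests on assumptions: with correlation 0.5 to 0.7 the variance falls by 15% to 25%, and with SD 12 to 18 the half-width for the higher dose is about 5 to 10 points, wider for the lower dose. The gain is a prespecified, baseline-adjusted estimate with its uncertainty shown, not a likely significant result. Severity is minor because the objective is exploratory; this is a cheap improvement.

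**What to change.** In SAP Tables 11 and 12 and sections 13.6.6.1 and 13.6.6.3, apply the NTDT-PRO ANCOVA to the TranQOL total (TDT) and to the SF-36 physical and mental component scores (both populations) at Weeks 24 and 36. Use treatment as factor and baseline score as covariate, and report the least-squares mean difference and 95% CI for each dose and the pooled dose versus placebo. Label the results exploratory and emphasise the interval.

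Name the analysis set explicitly. Tables 3 and 4 give ITT (mITT) for QoL, whereas SAP 13.6.6 gives per protocol for all exploratory efficacy endpoints; the ITT (mITT) set fits a randomised comparison.

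Derive the TranQOL total by the instrument's own scoring rule, with its missing-item rule stated. Keep the TranQOL domains and SF-36 scales descriptive.

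The cost is SAP wording and some model output, with no new data, visits or subjects. The downside is up to about 30 more unadjusted contrasts with wide intervals, in a plan that already makes no multiplicity adjustment (13.6.1). Rewording the objective as descriptive would also remove the mismatch, but would give up the placebo comparison on data already being collected.

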13.6.6.2 Imputation Methods for the Hb Endpoints for the NTDT Population

The following imputation rules will be applied for the exploratory efficacy endpoints related to Hb (Proportion of subjects who have an Hb increase of ≥ 1.0 g/dL from Baseline for ≥ 14 days in the absence of RBC transfusions, Number of subjects with increase from Baseline of 1.0 g/dL in mean Hb values at Week 24 and Week 36 compared to Baseline in the absence of transfusions, Duration of the mean Hb increase from Baseline of ≥ 1.0 g/dL over 36 weeks, and Proportion of subjects who have an increase from Baseline of ≥ 1.5 g/dL in mean of Hb values in the absence of transfusions):

1. For the number of subjects with increase from Baseline of 1.0 g/dL in mean Hb values at Week 24 and Week 36 compared to Baseline in the absence of transfusions endpoint, and the proportion of subjects who have an increase from Baseline of ≥ 1.5 g/dL in mean of Hb values in the absence of transfusions endpoints, subjects will be treated as non-responders for the Week 24 or Week 36 time point if they received an RBC Transfusion within the prior 8 weeks for that time point (Weeks 16-24 for the Week 24 time point, Weeks 28-36 for the Week 36 time point). For the duration of the mean Hb increase from Baseline of ≥ 1.0 g/dL over 36 weeks endpoint, an 8 week period following any transfusion will be excluded from the duration total. For the number of subjects and the proportion of subjects with an increase from Baseline endpoints, this means that the subject will not be included in the number or proportion of subjects with an increase.
2. If the subject received an RBC Transfusion during the time periods described above the Hb will be imputed as the last assessment prior to transfusion
3. If some of the Hb values are missing during any of the time periods, the duration of the non-missing values during that time period will be used for the duration of the mean increase from Baseline endpoint and the non-missing values during that time period will be used for the determination of the number or proportion of subjects with an increase from Baseline endpoints.

The number of subjects with imputed values for the exploratory efficacy endpoints and the reason for imputation will also be summarized.

